**Adherence:** All participants will receive 1:1 adherence counselling for PrEP with individualized barrier identification and problem-solving assistance. Participants in the dPEP arm will receive 1:1 adherence counselling as well as reminders on their daily PrEP tablet bottle as a reminder to assess personal need for dPEP on that day. A number of measures will be used to determine adherence:

**Self-reported measures:** Sexual behavior and, for those assigned to the dPEP arm, pill-taking behavior, will be measured by timeline follow-back calendar at each follow-up visit to assess exposures and dPEP use. Because dPEP is an exposure-driven medication, adherence is dependent on use of dPEP following each exposure.

**Real-time behavioral measurement (optional):** Weekly SMS will be sent in English, *KiSwahili* or *DhoLuo* as part of a momentary ecological assessment of adherence and exposure. Exposure (i.e., condomless sex) will be referred to by a code word for added privacy: for example, "How many times did you dance [have sex without a condom] this week?" [If in the dPEP arm] "How many times did you take dPEP this week?" We have used real-time SMS data collection in multiple prior PrEP studies in Kenya; cell phones are very common in Kenya (outnumbering citizens). Encrypted transmission, password protection to open the surveys, and immediate deletion permit sensitive data to be collected safely. Studies of PrEP demonstrated that there was improved comfort with reporting sexual behavior via SMS, though objective adherence measures were far superior to self-report.

**Objective measures:** Hair drug levels will be measured to more objectively assess quantitative exposures to dPEP, for several analyses. Hair samples (50-100 strands) will be collected following consent to collection and confirmed eligibility for hair collection (occipital hair >0.5cm in length with absence of bleaching) from all participants at each visit (Months 0/3/6/9/12). Hair samples will be shipped to [name] UCSF Hair Analytical Laboratory (HAL).

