### Statistical power and analysis

We propose a standard randomized superiority design, comparing dPEP to standard of care. The primary trial outcome will be the combined incidence of incident *C. trachomatis*, *N. gonorrhoeae*, and syphilis, compared between the randomization arms, to mirror the IPERGAY approach; analyses will also test each pathogen alone. We have been conservative in planning: first, we have planned for an STI incidence of 22% per year in the standard of care arm, which is less than the *C. trachomatis* incidence seen in our recent studies (**Table 3**) and second, we will calculate based on time to first incident STI alone, although we anticipate that some women will have repeat STIs contributing additional events and additional statistical power. We have planned for a 50% effect, comparable to the IPERGAY results and sufficiently great for public health benefit, but we anticipate that the *C. trachomatis* effect could be >50%, given universal susceptibility to doxycycline and

IPERGAY findings. With 80% power, 10% loss-to-follow-up, incidence of 22% vs. 11% (n=44 vs. 22 cases), and a two-sided alpha of 0.05, a sample size of n=550 is needed (n=275 per arm).

*Primary Analysis:*

We will analyze the composite endpoint of any of the three STIs as well as for *C. trachomatis* alone, and we will continue until there are sufficient *C. trachomatis* events (n=66) given the high incidence of this pathogen and its importance for reproductive morbidity (the consequence of which will be that the total number of events in the composite of *C. trachomatis*, *N. gonorrhoeae*, and syphilis will be greater than n=66). Analyses will be intention-to-treat, including women whether or not they continue dPEP (as well as whether or not they continue PrEP). STI incidence will be compared between arms using repeated measures analysis of proportions (e.g., generalized estimating equations [GEE]), given possibility of repeat infection within individuals. Per-protocol and adjusted analyses will be done as needed, controlling for potential confounders: demographics (e.g., age, education), sexual behavior (e.g., condom use, # partnerships), and beliefs (e.g., risk perception, dPEP/PrEP efficacy). SAS or R will be used.

*Secondary Analyses:*

Safety: Safety outcomes (i.e., AEs, tolerability, pregnancy, behavior) will be compared between arms using repeated measures analyses.

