### **3. STUDY DESIGN**

#### **3.1. Summary of Study Design**

Open label 1:1 randomized trial of dPEP versus standard of care. Participants assigned to dPEP will be instructed to take doxycycline 200 mg (two 100mg capsules) orally within 24 hours and up to 72 hours after each condomless sex act as frequently as daily if indicated but not more than once daily.

At Months 0/3/6/9, women randomized to dPEP will receive doxycycline, sufficient for nearly daily use for 3 months (i.e., 100 capsules). Unused capsules will be counted at each follow-up visit (Months 3/6/9/12) and additional doxycycline will be given to total up to 180 capsules if needed. The medication, doxycycline hydiate, will be purchased from a quality-controlled supplier and with consultation by the Kenya National AIDS and STI Control Programme. Participants will also be offered single- or multi-dose pill carriers for ease of dosing dPEP following exposures. All participants will receive quarterly visits for standard of care prevention services and collection of clinical and behavioral data, for a total of 12 months of follow-up.

**Study visits:** Every 3 months, study visits will include STI screening, behavioral questionnaires, hair sample collection, and swab collection for archived samples. Women may return to the study clinic for interim visits for any reason and will undergo STI testing and treatment if STI symptoms are present. Participants with a new STI diagnosis will return for prompt treatment, provided on-site. Laboratory testing will be conducted by staff blinded to randomization assignment, and STIs will be reviewed by an Endpoint Adjudication Committee blinded to treatment arm. All participants diagnosed with an STI will either receive same day treatment or return to the research clinic for treatment, using WHO/Kenya standard therapies, avoiding doxycycline options, and a second visit two weeks following completion of STI treatment will be done for test of cure; this mitigates potential risk to participants and the community if resistance is selected.

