### **7.5.3. Analyses of the Primary Efficacy Results while on study drug (Per protocol)**

For the per-protocol analysis, for each cohort the dPEP arm will be restricted to study time prior to the first discontinuation (> 2 weeks) of study drug documented on the study dPEP CRF. The evaluation of the impact of doxycycline on Any STI will use the same model as specified for the primary analysis, but also potentially adjusted for age, baseline STI, baseline and follow-up sexual risk (number of partners, nulliparous, contraceptive use, transactional sex).

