### Descriptive:

EchoMobile SMS data: Past-week use of dPEP by reported sex acts among dPEP study arm participants in a table over all follow-up time, excluding periods where participant is on a documented study drug hold.

Timeline follow-back calendar: Past 2-week (day -14 to -3) participant-reported dPEP coverage among those with reported sex, by scheduled visit and over all follow-up time, excluding visits where participant is on a documented study drug hold.

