### **8.5.2. Longitudinal adherence-effectiveness analysis:**

Hair samples collected at quarterly follow-up study visits for all treatment group participants will be analyzed for quantitative hair drug levels. Based on HIV PrEP studies, we assume that dPEP will either be used regularly or not at all and that underdosing will be a rare occurrence. Because quantifying doxycycline drug hair levels is not yet standardized, we will not describe true event-based adherence but rather use vs. non-use.

1. Doxycycline use (defined as detectable doxycycline in a hair sample – binary variable) will be analyzed using GEE to measure effect of dPEP use compared to nonuse in preventing STI cases (quarterly measure of any incident STI – binary variable).

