### **9.2. Contamination and non-use:**

Hair samples were collected at all study visits. A random 10% subset of all participants at enrollment visit and 10% subset of samples from follow up study visits from the standard of care group will be analyzed for doxycycline drug concentrations to summarize instances of doxycycline detection at study enrollment (prior to dPEP initiation) or in the standard of care group. All hair samples collected in follow up study visits in the treatment group will be analyzed for instances of doxycycline non-detection, i.e., non-use (excluding participants with no sexual exposure reported in the last month). The percentage of participants with doxycycline detected in standard of care group will be compared with percentage of participants with doxycycline detected in dPEP arm over time, quarterly.

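### SAP 8.5.2 item 1 relates hair-detected doxycycline to STI with no exposure condition and no covariate, so non-use mixes unexposed women with exposed women who did not dose

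*SAP*

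**What the plan says.** SAP 8.5.2 takes the quarterly follow-up hair samples of the dPEP arm and defines use as any detectable doxycycline. In item 1 this yes/no variable "will be analyzed using GEE to measure effect of dPEP use compared to nonuse in preventing STI cases", with any incident STI in the quarter as the outcome. The section concedes that "we will not describe true event-based adherence but rather use vs. non-use", because hair quantification is not standardised. Its one stated assumption is that women dose regularly or not at all, with underdosing rare. The hair population in SAP 5.2.6 adds no exposure condition.

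Dosing in this trial is event-driven. SAP 3.1 has women take doxycycline "within 24 hours and up to 72 hours after each condomless sex act", and the protocol's adherence section says: "Because dPEP is an exposure-driven medication, adherence is dependent on use of dPEP following each exposure".

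Other parts of the documents allow for exposure:

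- SAP 8.5.1 reports calendar coverage "among those with reported sex, by scheduled visit and over all follow-up time, excluding visits where participant is on a documented study drug hold".
- SAP 9.2 counts undetectable hair samples in the dPEP arm as "non-use (excluding participants with no sexual exposure reported in the last month").
- The per-protocol model in SAP 7.5.3 is "potentially adjusted for age, baseline STI, baseline and follow-up sexual risk (number of partners, nulliparous, contraceptive use, transactional sex").
- Protocol section 10.0, adherence paragraph, counts an undetectable hair level as non-adherence only alongside self-reported unprotected sex. It ends by committing adjusted analyses to the Aim 1 confounders. For the primary analysis these include "sexual behavior (e.g., condom use, # partnerships").

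**The concern.** A woman who follows the dosing instruction perfectly and has no condomless sex in the period covered by her hair sample has undetectable drug. Her STI risk is also low, for a reason unrelated to doxycycline. Item 1 puts her in the same reference group as a woman who had condomless sex and did not dose. The reference group's STI risk is diluted, and the comparison no longer isolates what non-use does to an exposed woman.

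This is the SAP's only hair-based model of dPEP use against STI, and it serves the protocol's stated hair aim of relating adherence to protection. If the intention-to-treat effect turns out small, readers will turn to this model to ask whether the drug failed or was not taken. As specified it cannot separate non-use from absence of exposure, yet its wording presents the result as an effect.

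**Working it through.** **1. No plan figure to reproduce.** SAP 8.5.2 gives no sample size, power or expected effect. The documents also do not say how many undetectable samples come from unexposed women, or what their STI risk is. The figures below are therefore ranges under assumptions. The true relative risk (RR) of 0.50 is borrowed from the 50% reduction in SAP 3.3.1.

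**2. Definitions (all assumed).**
- s = share of non-use quarters with no condomless sex: 10%, 25%, 50%.
- k = STI risk in those quarters relative to the untreated risk of users: 0, 0.25, 0.5. Values above 0 allow for misreported exposure or condom failure.
- h = untreated STI risk of exposed non-users relative to users; h = 1 means no other confounding.
- Users are taken to be exposed.

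Apparent RR = 0.50 / [(1 − s)·h + s·k]

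**3. Mixing alone (h = 1).**

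| s | k = 0.5 | k = 0.25 | k = 0 |
|---|---|---|---|
| 10% | 0.50/0.950 = 0.53 | 0.50/0.925 = 0.54 | 0.50/0.900 = 0.56 |
| 25% | 0.50/0.875 = 0.57 | 0.50/0.8125 = 0.62 | 0.50/0.750 = 0.67 |
| 50% | 0.50/0.750 = 0.67 | 0.50/0.625 = 0.80 | 0.50/0.500 = 1.00 |

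**4. Net direction.** The mixing is exactly offset when h = (1 − s·k)/(1 − s). For k from 0.5 to 0 this is 1.06 to 1.11 at s = 10%, 1.17 to 1.33 at s = 25%, and 1.5 to 2.0 at s = 50%. Above those values the drug looks stronger than it is. For s = 25% and k = 0.25:
- h = 0.75: 0.50/(0.5625 + 0.0625) = 0.80
- h = 1: 0.62
- h = 1.5: 0.50/(1.125 + 0.0625) = 0.42

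**5. Which look-back the restriction should use.** SAP 2.2.4 equates 1 cm of hair with 4 weeks of use, starting one week before the visit. SAP 8.5.2 item 2 uses the span from 5 weeks to 1 week before the visit. Restricting item 1 to any condomless sex in the past 3 months would not match this: a woman exposed only early in the quarter would pass the restriction and still correctly show no drug. If condomless acts follow a Poisson process with mean m per 13 weeks (an assumption), the share of exposed quarters with none in the 4-week window is

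(e^(−4m/13) − e^(−m)) / (1 − e^(−m)).

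For m = 4 this is (0.292 − 0.018)/0.982 = 28%. For m = 2 it is 47%, and for m = 8 it is 8%. The last-month rule of SAP 9.2 fits the hair window much better.

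**6. What the 9.2 rule alone would achieve.** It removes women with no sex but not women who always used condoms. Suppose it removes half (r = 0.5) of the unexposed non-use quarters. The remaining share is s′ = s(1 − r)/(1 − s·r) = 0.053, 0.143, 0.333. With k = 0.25 and h = 1, the apparent RR moves from 0.54, 0.62, 0.80 to 0.52, 0.56, 0.67.

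**The case against.** The strongest reply is that adjustment is already planned. The protocol's adherence paragraph, which contains the hair aim, commits adjusted analyses to the Aim 1 confounders, and these include condom use and partnerships. That stands: a reader who inferred from SAP 8.5.2 that the study never meant to adjust would be wrong. The gap is that the SAP, which should fix the model, does not carry the commitment into item 1.

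Second, SAP 9.2 already reports non-use among sexually exposed women from the same samples. It does, and that shows how common exposed non-use was. But 9.2 does not relate non-use to STI, and item 1 defines its groups by detection alone, so the exclusion does not transfer.

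Third, one might infer that no hair window is specified anywhere. Item 2 does specify one. What remains is that item 1 does not say it uses the same window, and that about 4 weeks of hair is set against a quarterly outcome.

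Fourth, SAP 8.5.2 already disclaims event-based adherence. Its reasons concern assay standardisation and underdosing, not absence of exposure, and item 1 still speaks of an effect.

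Finally, this is a non-randomised, within-arm secondary analysis, limited to women whose hair was assayed. That bounds the importance of the point but does not remove it.

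**Conclusion.** The point holds as a gap in the specification of one secondary analysis. Followed as written, SAP 8.5.2 item 1 gives a confounded estimate, because under event-driven dosing its reference group combines absence of exposure with non-use. A correction is worth making because it is cheap.

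The size rests wholly on assumed inputs. With a true RR of 0.50, mixing alone gives 0.57 to 0.67 when a quarter of non-use quarters are unexposed. The extreme value of 1.00 needs half of them unexposed and at zero risk.

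Two stronger readings are not supported. One is that the analysis will understate dPEP: that follows from this mechanism alone, but if exposed non-users are at higher underlying risk the bias can reverse, so the documents do not establish a net direction. The other is that the trial's efficacy conclusion is at risk: the primary comparison is by randomised arm and does not use hair results, so it is untouched.

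**What to change.** In SAP 8.5.2 item 1:

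- Apply the SAP 9.2 exclusion of women reporting no sexual exposure in the last month, narrowed to condomless sex where condom data exist for that window.
- Adjust for time-varying condom use and number of partners, as the protocol plans.
- State that item 1 uses the hair window given in item 2, and acknowledge that it covers about 4 weeks of a quarterly outcome interval.
- Exclude visits on a documented drug hold, as SAP 8.5.1 does.
- Keep the unrestricted model as a sensitivity analysis.
- Describe the result as an association.

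The cost is SAP wording and programming before database lock, with no new data collection. Fewer visits enter the model. Exposure then rests on self-report, which the protocol rates below objective measures. The protocol describes a 3-month calendar with condom use, but the SAP mentions only a calendar covering days −14 to −3 and condom use at last sex, so condom data for the hair window may be incomplete. Some residual confounding will remain.

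Separately, and of minor weight, two definitions should be reconciled. The coverage denominator is all days with sex in SAP 8.5.1 but condomless episodes in protocol section 10.0. The SMS code word for dancing means condomless sex in the protocol and any sex in SAP 8.5.1.

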#### Secondary analyses

2. Describe the relationship between quantitative tertials of doxycycline hair drug levels (low, medium, and high) and the number of dPEP doses reported in SMS in the 4-week time period of hair sample (5 weeks prior to study visit until 1 week prior to study visit) by generating a scatterplot and reporting the mean number of doses reported per quantitative category.
3. The mean hair drug concentration among hair samples collected at study visits when an incident STI (CT, NG, or TP, combined and per infection) was detected will be described and compared to study visits when no incident STI was detected among treatment group.

## **9. ADDITIONAL SECONDARY ENDPOINT ANALYSIS**

### **9.1. Changes in sexual frequency**

SMS surveys collected weekly ask all participants how many days of the last week they had sexual intercourse with responses ranging from 0-7. We will compare frequency of sexual activity over time to investigate whether they differ by arm using a GEE with Poisson distribution.

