## Rationale

### *Rationale for a randomized trial*

We posit that there is equipoise to conduct a randomized evaluation at this time: while dPEP has demonstrated efficacy in one trial, it was relatively small in size and limited to MSM in France. Data specific to women are needed to know if dPEP is effective and safe. Additionally, the potential disadvantages of dPEP, such as

antibiotic resistance, tolerability, and low adherence, have not been studied in women and justify the use of a control arm. Randomization in 1:1 allocation will be the most efficient for evaluating efficacy of dPEP and balancing unknown acceptability. Like IPERGAY, we propose that an open-label design allows for optimal evaluation of effectiveness. First, the open-label model directly addresses questions about acceptability, as participants will react to dPEP itself, not a blinded, potentially placebo version. Second, an open-label design is likely to result in greater (and more realistic) adherence – in placebo-controlled trials of PrEP among African women, adherence was very low, and subsequent qualitative studies found concerns about receiving a placebo as a principal reason, with greater adherence in recent open-label studies. Third, the design will directly allow assessment of sexual behavior changes (i.e., disinhibition) related to STI PEP, which could overwhelm dPEP's benefits and is only assessable if subjects know if they are actually taking active dPEP.

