## 6.0 STUDY PROCEDURES

	Study Visit Month	S	0	3	6	9	12
Study coordination							
Obtain informed consent Screen for inclusion/exclusion Randomization Collect updated contact information Reimbursement	Obtain informed consent	X					
	Screen for inclusion/exclusion	X	X				
	Randomization		X				
	Collect updated contact information	X	X	X	X	X	X
	Reimbursement	X	X	X	X	X	X
Questionnaires							
Demographic information Behavioral questionnaire HIV risk perception Social Harms and IPV Sexual behavior and exposure history PrEP adherence dPEP adherence (timeline follow-back calendar) Fertility intention Quality of Life	Demographic information	X	X				
	Behavioral questionnaire		X		X		X
	HIV risk perception	X	X	X	X	X	X
	Social Harms and IPV	X	X	X	X	X	X
	Sexual behavior and exposure history	X	X	X	X	X	X
	PrEP adherence	X	X	X	X	X	X
	dPEP adherence (timeline follow-back calendar)			X a	X a	X a	X a
	Fertility intention	X	X	X	X	X	X
	Quality of Life	X	X	X	X	X	X
Clinical Study Care							
Medication review General symptom assessment WHO pregnancy checklist STI symptom assessment Supply condoms Contraception counseling and provision/referral Risk reduction counseling dPEP pill count and refill	Medication review	X	X	X	X	X	X
	General symptom assessment		X	X	X	X	X
	WHO pregnancy checklist	X		X	X	X	X
	STI symptom assessment	X	X	X	X	X	X
	Supply condoms	X	X	X	X	X	X
	Contraception counseling and provision/referral	X	X	X	X	X	X
	Risk reduction counseling	X	X	X	X	X	X
	dPEP pill count and refill			X a	X a	X a	X a
Sample collection							
HIV testing (rapid test) Urine pregnancy testing (rapid test) Syphilis testing (serum RPR) Creatinine (serum) CT/NG testing and resistance (endocervical swabs) c Hair PrEP and doxycycline drug levels Trichomonas screening (vaginal swab)	HIV testing (rapid test)	X		X	X	X	X
	Urine pregnancy testing (rapid test)	X b	X	X b	X b	X b	X b
	Syphilis testing (serum RPR)		X	X	X	X	X
	Creatinine (serum)	X b					
	CT/NG testing and resistance (endocervical swabs) c	X	X	X	X	X	X
	Hair PrEP and doxycycline drug levels		X	X	X	X	X
	Trichomonas screening (vaginal swab)		X	X	X	X	X
Archive							

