#### *Mobile phone SMS (optional – for participants with a phone and who agree to optional SMS component):*

Participants who consent to SMS will receive weekly SMS sent in English, Kiswahili, or DhoLuo as part of a momentary ecological assessment of adherence and exposure. Exposure, i.e. have penatratve sex without a condom, will be referred to by a code word for added privacy: for example, "How many times did you dance this week?" If a participant is in the dPEP arm, they will receive a second SMS, "How many times did you take dPEP this week?" Encrypted transmission, password protection to open the surveys, and immediate deletion permit sensitive data to be collected safely.

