### **Instructions for evaluations**

#### *Questionnaires and Interviews:*

**Quantitative data:** Demographic and behavioral surveys will be administered at each visit, using questions we have used extensively in our prior trials (**Table 4**). All participants will complete questionnaires each study visit on facilitators and barriers to STI prevention and dPEP.

Table 4. Data collection on facilitators of and barriers to STI prevention and dPEP: all have been used in our prior work (Table 5)	
Structural	E=enrollment, Q=quarterly, 6=Month 6 visit, 12=Month 12 visit
Socioeconomic status	employment (E), income (E), presence of running water/electricity/metal roof/TV/phone at home (WAMI) (E)
Individual	
Demographic factors	age (E), race/ethnicity/tribe (E), educational level (E), time spent traveling for clinic visit (E, 6, 12)
Alcohol use	# days in last week consumed, rapid alcohol problems screen-quantity frequency (RAPS4-QF) (E, 6, 12)
Depression	somatization, obsessive-compulsive, interpersonal sensitivity, anxiety and depression (HSCL-D) (E, 6, 12)
HIV risk perception	what do you think is your risk of getting (giving) HIV and STIs from (to) your partner? (4 item Likert scale) (E, Q)
Prevention strategies	perceived dPEP efficacy for STI prevention, perceived PrEP efficacy for HIV prevention (E, Q)
Social Harms	physical, social and economic social harms (E, Q)
Dyadic	
Relationship	partnership status (E, Q), social support (Modified UNC-Duke) (E, 6, 12), partner violence (E, Q)
Sexual behavior	sex frequency (E, Q), condom use (E, Q), sexual power (E, 6, 12)
Fertility intention	# of children (E), current pregnancy (E, Q), goal # of children and fertility intentions (E, Q)
HIV stigma	scale plus disclosure (e.g., serodiscordant status) to family/friends/religious leaders & adverse effects (E, 6, 12)

**Sexual behavior questionnaire:** Participants will be asked to complete a sexual behavior questionnaire using timeline follow-back calendar to record number and type of sexual contacts (including condom use) in the past 3 months at each study visit.

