### **2.2.4. Adherence**

Adherence is only assessed in the dPEP arm

- Weekly SMS questions
  - Weekly questions collected in participants who opted in to SMS.
  - Number of days in the last 7 days when dPEP was taken
  - Number of days in the last 7 days when participants had sex or “danced”).
- Hair samples
  - Collected quarterly
    - Quantitative amount of doxycycline in 1cm segments from cut end to tip which corresponds with a 4-week period of dPEP use (starting 1 week ago).
- Self-report of coverage of sexual contacts in the prior 14 days to 3 days in the dPEP arm:
  - Quarterly (timeline follow-back) adherence questionnaire.

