#### **5.2.8. SMS responder population**

Participants who have responded to at least 4 SMS surveys

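### SAP 9.1 compares sexual frequency between arms only in women who opted in to SMS, and the SAP makes no by-arm comparison of the contact counts scheduled for all women

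*SAP*

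**What the plan says.** **The planned test.** SAP 9.1 takes its data from weekly SMS: "SMS surveys collected weekly ask all participants how many days of the last week they had sexual intercourse with responses ranging from 0-7". The test follows: "We will compare frequency of sexual activity over time to investigate whether they differ by arm using a GEE with Poisson distribution". The section names no analysis population, no rule for missing weeks and no second data source.

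**Who receives SMS.** SAP 2.2.4 describes the same data as "Weekly questions collected in participants who opted in to SMS". The protocol's SMS section limits it to an optional component, "for participants with a phone and who agree to optional SMS component", and gives the dPEP arm a second weekly question. The protocol's Risks/Benefits section lets a woman stop the messages on request. SAP 5.2.8 defines a responder population, "Participants who have responded to at least 4 SMS surveys", but 9.1 does not cite it.

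**Other behaviour data.** The protocol's sexual behaviour questionnaire uses a "timeline follow-back calendar to record number and type of sexual contacts (including condom use) in the past 3 months at each study visit". Its adherence section limits only the pill-taking part of the calendar to the dPEP arm. The schedule in Protocol 6.0 lists sexual behaviour and exposure history at screening and at Months 0, 3, 6, 9 and 12 with no arm footnote.

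**What the SAP does with them.** SAP 8.5.1 uses the calendar for dPEP-arm coverage only, over days -14 to -3. SAP 9.1.1 compares condom use at last sex by arm from a quarterly survey that does not depend on SMS. SAP 7.5.3 may use number of partners as an adjustment variable. No section compares contact counts or partners between arms as an outcome.

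**The concern.** Behaviour change is a central question in this trial. The protocol's rationale gives three reasons for an open-label design, and the third is that "the design will directly allow assessment of sexual behavior changes (i.e., disinhibition) related to STI PEP"; it adds that such changes could outweigh the benefit of dPEP. Protocol 10.0 lists behaviour among the safety outcomes to be compared between arms with repeated measures.

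The only planned comparison of frequency rests on a subset that the SAP describes as everyone. Two things could go wrong. First, the result describes women with phones who agreed to be texted, while a reader of 9.1 would take it to describe the whole cohort. Second, answering week by week happens after randomisation, in women who know their arm and receive different numbers of questions. If the less sexually active women stop answering in one arm only, the arms will appear to differ when they do not, or a real difference will be hidden.

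The condom item does not fill the gap. It is a single binary response that groups women who had no sex with those who used a condom, so it shows neither frequency, nor number of partners, nor condomless acts.

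**Working it through.** No figure in the plan is in dispute. The check compares the texts and then sizes the effect over a range of assumptions.

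**1. Texts side by side.**

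| Feature | SMS | Contact counts |
|---|---|---|
| Who | Opt-in, phone needed, may stop (Protocol SMS and Risks/Benefits sections; SAP 2.2.4) | Participants in general; only pill-taking limited to dPEP (Protocol questionnaire and adherence sections) |
| When | Weekly; no pre-randomisation value described | Screening, Months 0, 3, 6, 9, 12 (Protocol 6.0) |
| What | Protocol: number of times, sex without a condom. SAP 9.1: days with intercourse, 0 to 7 | Number and type of contacts with condom use, past 3 months |
| By-arm comparison in SAP | Yes, 9.1 | None |

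The third row is a further mismatch: the protocol's text message and SAP 9.1 do not describe the same quantity.

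**2. Precision.** Inputs: 223 women per arm (SAP 3.3.1) and opt-in share *f*, which is an assumption. With one mean per woman, the interval widens by 1/√*f*. The smallest difference detectable with 80% power at two-sided 0.05 is (1.960 + 0.842) × √(2/(223*f*)), in SDs of a woman's mean days per week.

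| *f* | Women of 446 | CI widening | Detectable difference (SD) |
|---|---|---|---|
| 0.3 | 134 | 1.83 | 0.484 |
| 0.5 | 223 | 1.41 | 0.375 |
| 0.7 | 312 | 1.20 | 0.317 |
| 0.9 | 401 | 1.05 | 0.280 |
| 1.0 | 446 | 1.00 | 0.265 |

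The table compares partial SMS with complete SMS. It does not compare SMS with the calendar.

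**3. Generalisability.** The difference in all women is *f* × (difference in responders) + (1 - *f*) × (difference in non-responders). Suppose responders show no difference and non-responders differ by an assumed 0.5 day per week. The all-women difference that SMS would miss is (1 - *f*) × 0.5 = 0.35, 0.25, 0.15 or 0.05 day per week at *f* = 0.3, 0.5, 0.7 or 0.9.

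**4. Differential response, illustration only.** Set the true mean frequency to 1 in both arms. Suppose 20% of dPEP women, with half the average frequency, do not respond, and all controls do. The dPEP responders' mean is (1 - 0.2 × 0.5)/0.8 = 0.9/0.8 = 1.125, so the arm ratio is 1.125 with no true difference. None of these inputs is in the documents. The opposite pattern would bias the other way.

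**5. Trichomonas as a possible check.** NAAT is scheduled at Months 0, 3, 6, 9 and 12, and the SAP does not analyse it. Assume 10% to 20% of about 200 women per arm test positive in a year, giving *d* = 20 to 40 events per arm. Then SE(log ratio) = √(2/*d*) = 0.316 to 0.224, and the 95% CI factor is exp(1.96 × SE) = 1.86 to 1.55. With a true ratio of 1, the interval would still include a 50% rise.

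**The case against.** The strongest reply has four parts.

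*All participants* may simply mean both arms, since the protocol sends the sex question to every SMS participant and the second question to dPEP only. That is plausible, but 9.1 does not say so, and its wording conflicts with SAP 2.2.4. The wording needs correcting in any case.

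A reader might infer that the SMS comparison has lost the protection of randomisation. The documents do not support this. They do not say when opt-in happens. If it precedes randomisation, the opt-in subset is still a randomised comparison, and opt-in costs precision and generalisability, not validity. What stands is that later response could differ by arm, and 9.1 plans nothing that would show it.

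A reader might also infer that the calendar should replace SMS. The protocol reports greater comfort in disclosing sexual behaviour by SMS, and a calendar completed at a visit carries 3-month recall and in-person reporting, which could themselves differ by arm. This stands: the two sources have different weaknesses.

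Finally, control-arm calendar data may be incomplete. The only schedule row that names the calendar is dPEP adherence, marked intervention arm only. Against that, the questionnaire and adherence text and the unrestricted exposure-history row point to both arms, and SAP 7.5.3 presupposes follow-up partner counts. Confirmation is still needed.

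The SAP also says that it details only primary and key secondary objectives, so its silence does not cancel the protocol's promised comparison of behaviour. But that promise then has no specified outcome or model beyond 9.1 and 9.1.1.

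**Conclusion.** The concern holds in a limited form. SAP 9.1 misdescribes its population, does not plan to show whether response differs by arm, and leaves contact counts scheduled in both arms without a between-arm comparison. This is a cheap improvement to a secondary analysis.

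Its size depends on an opt-in rate that the documents do not give: at 90% opt-in the loss of precision is slight, and at 50% the interval is 1.41 times wider. The 1.125 ratio shows a mechanism and is not an estimate.

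One further inference should be resisted: that Trichomonas could serve as a negative-control outcome in a formal model. The documents do not propose it as a behaviour marker; the one they name is Y chromosome DNA from archived vaginal swabs. The protocol also uses metronidazole both to treat Trichomonas and in the regimen for complicated STI, so if dPEP lowers STIs, metronidazole use could differ by arm. Together with the wide interval, this leaves room for a descriptive tabulation only.

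**What to change.** Before database lock:

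1. In SAP 9.1, replace *all participants* with *participants in both arms who opted in to SMS*. State whether the 5.2.8 responder population applies, and describe the quantity asked so that it matches the message sent.
2. Report opt-in and weekly response by arm.
3. Confirm that the control-arm calendar, including Month 0, was completed as the protocol's questionnaire and adherence sections state. Check completeness only, not values by arm.
4. Add an ITT comparison by Poisson GEE with robust standard errors of (a) quarterly reported condomless acts and (b) number of partners at Months 3 to 12, each adjusted for its Month 0 value. Present it alongside the SMS result without ranking one source above the other, and state the recall and reporting limits.
5. Optionally, tabulate Trichomonas positivity by arm and visit, as description only.

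The cost is SAP wording, one response table, a completeness check and two models on data that the protocol already schedules. No visit, sample or primary analysis changes. The added analysis brings 3-month recall and in-person reporting with it.
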